10. MEASUREMENT OF EFFECT

Objective response rate is the primary endpoint of the expansion cohort of this trial and participants will be assessed by RECIST v1.1 criteria. For the purposes of this study, participants should be reevaluated every 8 weeks. In addition to a baseline scan, confirmatory scans should also be obtained at least 4 weeks following initial documentation of an objective response.

10.1 Antitumor Effect– Solid Tumors

Response and progression will be evaluated in this study using the new international criteria proposed by the Response Evaluation Criteria in Solid Tumors (RECIST) Committee v. 1.1⁵⁷. Changes in only the largest diameter (unidimensional measurement) of the tumor lesions are used in the RECIST criteria.

10.1.1 Definitions

Evaluable for toxicity. All participants who receive at least one dose of study treatment will be evaluable for toxicity from the time of their first treatment.

Evaluable for objective response. All participants who receive at least one dose of study treatment will be evaluable for response from the time of their first treatment. These participants will have their response classified according to the definitions stated below.

10.1.2 Disease Parameters

Measurable disease. Measurable disease is the presence of at least one (1) lesion that can be accurately measured in at least one dimension with longest diameter ≥ 20 millimeters (mm) using conventional techniques (CT, MR1, x-ray) or ≥ 10 mm with spiral CT scan. Measurable lesions must be at least 2 times the slice thickness in mm. All tumor measurements must be recorded in millimeters (or decimal fractions of centimeters).

Malignant lymph nodes: To be considered pathologically enlarged and measurable, a lymph node must be ≥ 15 mm in short axis when assessed by CT scan (CT scan slice thickness recommended to be no greater than 5 mm). At baseline and in follow-up, only the short axis will be measured and followed.

A lesion in a previously irradiated area is not eligible for measurable disease unless there is objective evidence of progression of the lesion prior to study enrollment. Lesions in previously irradiated areas must be clearly identified as such.

Non-measurable disease. All other lesions (or sites of disease), including small lesions (longest diameter <20 mm with conventional techniques or <10 mm using spiral CT scan), are considered non-measurable disease. Bone lesions, leptomeningeal disease, ascites, pleural/pericardial effusions, lymphangitis cutis/pulmonis, inflammatory breast disease,

abdominal masses (not followed by CT or MRI), and cystic lesions are all considered non-measurable.

Target lesions. All measurable lesions up to a maximum of 2 lesions per organ and 5 lesions in total, representative of all involved organs, should be identified as target lesions and recorded and measured at baseline. Target lesions should be selected on the basis of their size (lesions with the longest diameter) and their suitability for accurate repeated measurements (either by imaging techniques or clinically). A sum of the longest diameter (LD) for all target lesions will be calculated and reported as the baseline sum. If lymph nodes are to be included in the sum, then as noted above, only the short axis of the lymph node is added into the sum. The baseline sum will be used as the reference by which to characterize the objective tumor response.

Lymph nodes. Lymph nodes identified as target lesions should always have the actual short axis measurement recorded (measured in the same anatomical plane as the baseline examination), even if the nodes regress to below 10mm on study. This means that when lymph nodes are included as target lesions, the 'sum' of lesions may not be zero even if complete response criteria are met, since a normal lymph node is defined as having a short axis of <10mm. Case report forms or other data collection methods may therefore be designed to have target nodal lesions recorded in a separate section where, in order to qualify for CR, each node must achieve a short axis <10mm. For PR, SD and PD, the actual short axis measurement of the nodes is to be included in the sum of target lesions.

Non-target lesions. All other lesions (or sites of disease) including any measurable lesions over and above the 10 target lesions should be identified as non-target lesions and should also be recorded at baseline. Measurements of these lesions are not required, but the presence or absence of each should be noted at each follow-up.

10.1.3 Methods for Evaluation of Measurable Disease

All measurements should be taken and recorded in metric notation, using a ruler, calipers, or digital measurement tool. All baseline evaluations should be performed as closely as possible to the beginning of treatment and never more than 4 weeks before the beginning of the treatment.

The same method of assessment and the same technique should be used to characterize each identified and reported lesion at baseline and during follow-up. Imaging-based evaluation is preferred to evaluation by clinical examination when both methods have been used to assess the anti-tumor effect of a treatment.

Clinical lesions. Clinical lesions will only be considered measurable when they are superficial (e.g., skin nodules and palpable lymph nodes). For the case of skin lesions, documentation by color photography, including a ruler to estimate the size of the lesion, is recommended.

Chest x-ray. Lesions on chest x-ray are acceptable as measurable lesions when they are clearly defined and surrounded by aerated lung; however, CT is preferable.

Conventional CT and MRI. These techniques should be performed with cuts of 10 mm or less in slice thickness contiguously. Spiral CT should be performed using a 5 mm contiguous reconstruction algorithm. This applies to tumors of the chest, abdomen, and pelvis. Head and neck tumors and those of extremities usually require specific protocols.

10.1.4 Response Criteria

10.1.4.1 Evaluation of Target Lesions

Complete Response (CR): Disappearance of all target lesions.

Partial Response (PR): At least a 30% decrease in the sum of the longest diameter (LD) of target lesions (or short axis for lymph nodes), taking as reference the baseline sum.

Progressive Disease (PD): At least a 20% increase in the sum of the target lesions, taking as reference the smallest sum recorded since the treatment started or the appearance of one or more new lesions (new lesions must be $>$ slice thickness).

Stable Disease (SD): Neither sufficient shrinkage to qualify for PR nor sufficient increase to qualify for PD, taking as reference the smallest sum since the treatment started.

Unknown (UN): Assessment of target lesions cannot be made due to insufficient or unevaluable data. In this case, a concise explanation must be given.

Note: If tumor response data is missing, an overall assessment cannot be done. However, if there is missing or unevaluable data for non-target lesions, but data is available for all target lesions, the overall response for that time point will be assigned based on the sum of all target lesions. Additionally, the assessment of CR cannot be made if there is missing or unevaluable data for non-target lesions. In this case, the overall assessment would be PR.

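### The progression rule sets no minimum absolute growth and has no precedence over nodal complete response, so in small node-only residual disease one scan can meet both definitions

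*Combined protocol and SAP*

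**What the plan says.** Section 10.1.4.1 calls target-lesion progression on "At least a 20% increase in the sum of the target lesions, taking as reference the smallest sum recorded since the treatment started". The only size floor in that definition is for new lesions ("new lesions must be $>$ slice thickness"); growth of the target sum has none. The same section gives "Complete Response (CR): Disappearance of all target lesions", with no exception for nodes.

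Section 10.1.2 treats nodes differently. It regards a node under 10 mm as normal and says that "in order to qualify for CR, each node must achieve a short axis <10mm". It accepts that the sum may therefore be above zero at CR, and adds: "For PR, SD and PD, the actual short axis measurement of the nodes is to be included in the sum of target lesions".

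The table in Section 10.1.4.3 maps target CR to overall CR and target progression to overall progression. It does not say what happens if both are met.

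On which text governs, Sections 10, 10.1 and 14.4 name RECIST 1.1, while Section 10.1.1 says response is classified by the definitions that follow it. Neither is given priority.

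Section 10.1.2 also caps target lesions ("All measurable lesions up to a maximum of 2 lesions per organ and 5 lesions in total") but describes non-target lesions as including "any measurable lesions over and above the 10 target lesions".

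**The concern.** With a small reference sum, 20% is a very short distance. Because normalised nodes stay in the sum, a patient whose only remaining target disease is a normal-sized node can be classified as CR under one section and as progression under another, on the same measurement.

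A progression call ends protocol treatment (Section 5.6), progression-free survival (Section 10.1.6) and duration of response (Section 10.1.5), and closes the window for best overall response (Section 10.1.4.3). Section 10 asks for a confirmatory scan at least 4 weeks after a first response. A spurious progression call on that scan can remove a responder from the primary endpoint, which is judged on a small count: at least 3 of 18, then at least 5 of 26.

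**Working it through.** **1. The plan's own figures.** Section 14.1 uses 18 then 8 eligible treated patients, continuing on at least 3 responses and declaring promise on at least 5. Early stopping is P(X1 ≤ 2). The chance of declaring promise is the sum over x ≥ 3 of P(X1 = x) × P(X2 ≥ 5 − x). At a 10% response rate this gives 0.734 and 0.099; at 30% the power is 0.904. All agree with the plan. The point concerns the response calls that feed this design, not its arithmetic.

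**2. Growth that triggers progression** = 0.20 × smallest sum.

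| Smallest sum (mm) | Growth needed (mm) |
|---|---|
| 5 | 1.0 |
| 7 | 1.4 |
| 8 | 1.6 |
| 10 | 2.0 |
| 10.5 | 2.1 |
| 25 | 5.0 |
| 70 | 14.0 |

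So 1 to 2 mm suffices only at sums of 10 mm or less. Such sums are reachable: a 10 mm lesion (the smallest measurable on spiral CT) with a minimum partial response measures 7 mm. A 15 mm node (the smallest measurable) with a minimum partial response measures 10.5 mm, just outside.

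**3. Double classification.** A single node with nadir N meets the 20% rule and stays under 10 mm if 1.2 × N < 10, so N < 8.33 mm. Take 16, 8, 9.6 mm:
- At 8 mm the node has shrunk by 50%. That is CR under Section 10.1.2 and at least partial response under Section 10.1.4.1, so a response either way.
- At 9.6 mm it is still under 10 mm (CR, Section 10.1.2) and up 1.6/8 = 20% (progression, Section 10.1.4.1).

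This needs every non-nodal target gone and every target node under 10 mm.

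**4. An absolute minimum alone does not cure this.** With a 5 mm minimum, one node going from 4 to 9 mm (+5 mm, +125%), or two nodes each going from 6 to 9 mm (12 to 18 mm, +6 mm, +50%), still meets both definitions. A precedence rule is also needed.

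**5. Reading noise.** The documents give no reading error. Assume independent normal errors with SD σ per lesion, k lesions, true sum s unchanged. Progression is read when the second sum is at least 1.2 times the first, so

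P = 1 − Φ(0.2s / (σ√(2.44k))), where 2.44 = 1 + 1.2².

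For one 8 mm node:
- σ = 1.0: 1.6/1.562 = 1.02, P = 15%
- σ = 0.5: 1.6/0.781 = 2.05, P = 2%
- σ = 1.5: 1.6/2.343 = 0.68, P = 25%

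With a 5 mm minimum added, P is at most 1 − Φ(5/(σ√2)): 0.02% at σ = 1.0 and 0.9% at σ = 1.5.

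**6. Larger sums.** The same model was simulated over three follow-up scans, with the running minimum including baseline as reference and σ = 1. One 30 mm lesion gives under 0.1%. Two 15 mm lesions give just under 2%. Three 10 mm lesions give 6.5%, or 1.3% per scan (6/√7.32 = 2.22). At sums above 25 mm a 5 mm minimum never binds, because 20% already exceeds 5 mm. Whatever noise remains there is not due to the missing minimum.

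**7. Effect on the decision.** If a fraction f of true responders were lost at confirmation, power at a true 30% rate is the Section 14.1 calculation at 0.30 × (1 − f): 0.875 for f = 5%, 0.839 for 10% and 0.747 for 20%. With a 15% loss among exposed responders, f = 5% needs 0.05/0.15 = 33% of responders to be exposed and f = 10% needs 67%. The value f = 20% cannot be reached (133%).

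**The case against.** The strongest reply is that RECIST 1.1 is adopted by name, including for measurable disease in Section 3.3.2 and for progression-free survival and duration of response in Section 14.4, so Section 10.1.4.1 is only an incomplete paraphrase. That may be the intent. But Section 10.1.1 directs classification to the local definitions, and nothing says which text wins. The standard is not part of the documents, so its content cannot be used here to fill the gap.

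A second reply is that checking CR before the sum is the natural reading, since Section 10.1.2 uses the sum only for the other categories. That is a reasonable reading, but it is not written down, and Section 10.1.4.1 does not carry the node rule at all.

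Several stronger readings are tempting, and the documents do not support them:
- **Baseline is excluded from the progression reference**, because it precedes treatment. Section 10.1.2 makes the baseline sum the reference for objective response, and Section 10.1.4.3 allows progression with no earlier stable disease or response. Target growth could hardly produce that at a first scan if baseline did not count.
- **Sites will compute different sums** because of the 5 and 10 target limits. Only target lesions enter the sum, and these are capped at 5. The 10 sits in the non-target definition, which already takes in all other lesions. It is a leftover number.
- **False progression is common.** Over three scans at σ = 1, a single unchanged lesion gives 37% at 10 mm, 12.5% at 15 mm and 51% for an 8 mm node. These are worst cases. The first two describe lesions that have not responded, so they bear on progression-free survival. Progression after a confirmed response cannot undo it, so the primary endpoint depends on the confirmatory scan only.
- **CT resolution dictates 5 mm.** Section 10.1.3 says "Spiral CT should be performed using a 5 mm contiguous reconstruction algorithm", but it also allows conventional cuts of up to 10 mm, and slice spacing is not the error of an in-plane diameter. The 5 mm figure is a choice.

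**Conclusion.** The inconsistency is real and rests on the text alone: Sections 10.1.2 and 10.1.4.1 give different CR definitions, the 20% rule has no absolute minimum, and no precedence is stated. Its reach is narrow. Double classification is confined to patients whose remaining target disease is nodes under 10 mm, and a 1 to 2 mm trigger to smallest sums of 10 mm or less.

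For an unchanged 8 mm node, a false progression call at one confirmatory scan has a probability of about 15% (2% to 25%). This rests on an assumed reading SD of 1 mm (0.5 to 1.5) and normal, independent errors. One- or two-lesion sums of 30 mm carry about 2% or less over three scans at SD 1 mm. The documents do not give the share of patients with small or node-only residual disease, so the power losses above are scenarios, not estimates. The Section 14.1 design figures are not in question. This should be corrected as an inconsistent endpoint rule; it is not evidence that the response endpoint is unreliable overall.

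**What to change.** Reconcile Section 10.1 with the cited standard and state which text governs. Then:

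1. In Section 10.1.4.1, require for target-lesion progression both an increase of at least 20% and a stated absolute minimum increase (for example 5 mm) over the smallest sum on study. Say, as a clarification, that baseline counts.
2. In the same section, define target-lesion CR as disappearance of all non-nodal targets with every target node under 10 mm in short axis.
3. State that target-lesion CR takes precedence over the 20% sum rule for as long as that holds. Limit this to the target-lesion category: new lesions or non-target progression still give overall progression under Section 10.1.4.3.
4. In the non-target definition of Section 10.1.2, change 10 to 5 as a clerical edit.

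The cost is wording in Section 10.1 and on the response form, with no added scans. The downside is that small true growth in a very small lesion may be called progression one scan later.

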5.2.4 Every 8 weeks

Radiologic disease evaluation: Radiological assessments include a CT or X-ray of the chest and abdominal and pelvic CT or MRI scan. In patients with osseous lesions, bone X-rays and/or bone scans should be obtained. Tumor measurements should occur every 8 weeks (within 7 days prior to day 1 of the subsequent cycle).

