10.1.4.2 Evaluation of Non-Target Lesions

Complete Response (CR): Disappearance of all non-target lesions and normalization of tumor marker level.

Note: If tumor markers are initially above the upper normal limit, they must normalize for a subject to be considered in complete clinical response

Incomplete Response/Stable Disease (SD): Persistence of one or more non-target lesions and/or maintenance of tumor marker level above the normal limits.

Progressive Disease (PD): Appearance of one or more new lesions (new lesions must be $>$ slice thickness) and/or unequivocal progression of existing non-target lesions.

Unknown (UN): Assessment of target lesions cannot be made due to insufficient or unevaluable data. In this case, a concise explanation must be given.

Note: Although a clear progression of "non-target" lesions only is exceptional, in such circumstances, the opinion of the treating physician should prevail and the progression status should be confirmed at a later time by review of the Principal Investigator (or Protocol Chair). Additionally, the cytological confirmation of the neoplastic origin of any effusion that appears or worsens during treatment is mandatory to differentiate between stable or progressive disease status.

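### A new lesion is progression only if it exceeds the slice thickness, a threshold that varies with the imaging used, is undefined on some methods, and is absent from the best-response table

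*Combined protocol and SAP*

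**What the plan says.** The progression definition for target lesions (10.1.4.1) includes new lesions, with the qualifier "new lesions must be $>$ slice thickness". The definition for non-target lesions (10.1.4.2) repeats it: "Appearance of one or more new lesions (new lesions must be $>$ slice thickness) and/or unequivocal progression of existing non-target lesions".

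Slice thickness is set in 10.1.3. For conventional CT and MRI: "These techniques should be performed with cuts of 10 mm or less in slice thickness contiguously". For spiral CT: "Spiral CT should be performed using a 5 mm contiguous reconstruction algorithm".

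The scheduled imaging in 5.2.4 leaves the modality open: "Radiological assessments include a CT or X-ray of the chest and abdominal and pelvic CT or MRI scan". It adds: "In patients with osseous lesions, bone X-rays and/or bone scans should be obtained". Section 10.1.3 also accepts superficial clinical lesions, with skin lesions documented by photograph and ruler.

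The best-response table in 10.1.4.3 has a column for new lesions. Its last row gives PD whenever that column is Yes, whatever the targets and non-targets show, and states no size condition.

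Best overall response is read up to progression (10.1.4.3). PFS and duration of response end at progression (10.1.5, 10.1.6, 14.4).

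**The concern.** A progression criterion should depend on the disease and not on the machine. Here the threshold is a property of the scan, it differs between permitted techniques, and several permitted methods do not have it at all. Two assessors who both follow the protocol, one reading 10.1.4.1 and the other the 10.1.4.3 table, can score the same scan differently.

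Progression feeds the primary endpoint and two secondary ones. If a new lesion appears before or together with target shrinkage, the table gives PD while the size condition can leave PR or SD. If it appears after a confirmed response, responder status is unchanged, but PFS and duration of response run on until something else qualifies as progression.

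**Working it through.** **Step 1. Apply the size condition to example lesions.** The lesion sizes are chosen for illustration. The thresholds come from 10.1.3.

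| New lesion | Spiral CT, 5 mm | Conventional CT or MRI at the 10 mm limit | X-ray, bone scan, skin | 10.1.4.3 table |
|---|---|---|---|---|
| 8 mm | 8 > 5: PD | 8 < 10: not PD | undefined | PD |
| 10 mm | 10 > 5: PD | 10 is not > 10: not PD | undefined | PD |

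The 10 mm lesion reaches the size at which 10.1.2 calls a lesion measurable on spiral CT, yet it would not count as new disease on 10 mm cuts.

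**Step 2. Direction.** The condition removes lesions from the PD category and adds none. Any effect is therefore towards fewer or later progressions.

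**Step 3. Reproduce the plan's own design figures.** The inputs, from 14.1, are 18 eligible treated patients in stage 1, continuation with 3 or more responses, 8 more patients, and success with 5 or more of 26. With X ~ Bin(18, p) and Y ~ Bin(8, p):

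P(promising) = Σ over x ≥ 3 of P(X = x) · P(Y ≥ 5 − x)

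At p = 0.10:
- x = 3: 0.1680 × 0.1869 = 0.0314
- x = 4: 0.0700 × 0.5695 = 0.0399
- x ≥ 5: 0.0282
- Sum: 0.0995. The plan states 0.099.

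Early stopping is P(X ≤ 2) = 0.7338 (plan: 0.734). At p = 0.30 the power is 0.9037 (plan: 0.904). All three reproduce with 26 patients.

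**Step 4. Illustration: exactly one patient is a certain false responder and the other 25 respond at 10%.**

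False responder in stage 1, with X ~ Bin(17, 0.10) and stage 1 total X + 1:
- total 3: 0.2800 × 0.1869 = 0.0523
- total 4: 0.1556 × 0.5695 = 0.0886
- total ≥ 5: 0.0826
- Sum (unrounded terms): 0.224

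False responder in stage 2, with X ~ Bin(18, 0.10), 7 other stage 2 patients and one response assured:
- x = 3: 0.1680 × 0.5217 = 0.0876
- x = 4: 0.0700 × 1 = 0.0700
- x ≥ 5: 0.0282
- Sum: 0.186

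One reclassified patient at the boundary, 4/26 (15.4%) to 5/26 (19.2%), also reverses the decision. Neither result says how often the size condition would produce such a patient. The documents give no frequency for new lesions at or below the slice thickness and no distribution of cut thickness or modality.

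**The case against.** Several defences have force.

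- **Responses are to be confirmed.** Section 10 calls for a repeat scan at least 4 weeks after a first response, 10.1.4.3 makes best response depend on confirmation, and 14.4 refers to confirmed responders. (The confirmation cell in the main PR row reads as blank, which may be a merged cell lost in extraction.) A false responder therefore needs target shrinkage of at least 30% and a new lesion still at or below the threshold at the confirmatory scan. This stands, and it makes the effect on the primary endpoint less likely than the effect on PFS.
- **The 10 mm figure is a ceiling.** Spiral CT is set at 5 mm, and nothing shows that any site uses thicker cuts. This also stands. The same-technique rule in 10.1.3 limits drift within a patient for lesions already identified, but it does not align patients or sites.
- **The condition has a purpose.** Findings smaller than a slice are unreliable, and counting them risks false progression. That is fair, but a requirement that the lesion be unequivocal meets the same need without tying the endpoint to the scanner.
- **The table may be meant to be read with the definitions,** so that a lesion at or below slice thickness is entered as No. The table does not say so, and on that reading the dependence on technique remains.

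Some stronger readings are tempting but not supported.

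- A reader might infer that a new lesion on X-ray or bone scan can never be progression. The text leaves the condition undefined there, and the 10.1.4.3 table would still count the lesion. Growth of known bone disease has its own route, "and/or unequivocal progression of existing non-target lesions", although that does not cover a separate new bone lesion.
- A reader might infer a fixed 56-day delay per affected progression, or 1/26 = 3.8 points of 4-month PFS per patient. Both assume that nothing else triggers PD and that the lesion qualifies at the next 8-weekly scan. The 3.8 points also need the move to be from week 16 to week 24, with no earlier censoring.
- A reader might set the rule "Measurable lesions must be at least 2 times the slice thickness in mm" against the 15 mm node threshold and infer an eligibility conflict. Section 10.1.2 recommends slices of at most 5 mm for nodes. Then 2 × 5 = 10 mm, below 15 mm, and the conflict disappears.

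**Conclusion.** The point holds as an inconsistency in the endpoint definition. Sections 10.1.4.1 and 10.1.4.2 impose a size condition that varies between permitted techniques (5 mm, or anything up to 10 mm), is undefined on non-sectional methods, and does not appear in the 10.1.4.3 table. Followed literally, it can withhold PD from a clear new lesion.

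The direction is known: longer PFS and duration of response and, less often, an extra responder. The size is not known. It is small if scans are 5 mm spiral CT and grows with the use of thicker cuts, MRI or non-sectional imaging, on which the documents are silent. The range 0.186 to 0.224, against 0.0995, assumes one false responder with certainty. Any scoring error that creates one false responder would give the same figures, so they show how sensitive the decision rule is and do not estimate the effect of this wording.

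**What to change.** Delete the slice-thickness parenthesis in 10.1.4.1 and 10.1.4.2, so that both agree with the 10.1.4.3 table. In its place state that:

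- a new lesion is PD when it is unequivocal and not explained by a change in imaging technique, on any modality;
- an equivocal new lesion is re-assessed at the next scheduled scan and, if confirmed, PD is dated to its first appearance.

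The cost is wording in the protocol and the response form, with no added scans. The downside is that reader judgement replaces a size cut-off for small lesions. No change to the permitted cut thickness is needed for this point.
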